month prior to implementation, we will train home visitors and mental health professionals on MB. We will stagger implementation in two waves so that only half the sites are implementing at once. This will allow our Intervention Coordinator to focus her efforts on ensuring attendance at intervention groups and fidelity to intervention protocols. Study recruitment and implementation of all prenatal MB sessions will be completed by the 4th quarter of Year 2. This recruitment schedule will allow us to complete all postnatal MB sessions and follow-up data collection by the middle of Year 3, allowing study investigators to analyze data and prepare to disseminate study findings to both academic and community stakeholders.

Participant Screening: Participants will initially be screened for eligibility criteria by their home visiting program sites. Upon permission from the potential study participant, program sites will fill out a referral form, which will include the potential study participants name and contact information, and send it to the research team. Once the program sites refer potential study participants, a member of the study team will call the participant using the “Phone Script for Referrals” to screen the potential study participant for eligibility criteria and move forward with the consent process either via telephone or REDCap survey link.

Participant Outcomes Surveys: Participant outcomes will be collected at four time points—baseline, post-intervention, 12 weeks postpartum, and 24 weeks postpartum. Participants will receive \$20 remuneration at the baseline, 12-week and 24-week assessments. The MMS and EPDS will be administered to all clients during their baseline surveys. This information will be used for data analytics but not as an exclusion criteria. Data will only be collected from study participants who have consented to participate in the study.

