Home Visitors: We will recruit 72 home visitors from 42 participating HV programs throughout the state of Illinois and adjacent states. All HV programs recruit women at high risk for poor pregnancy and/or parenting outcomes via referrals from prenatal care clinics, community outreach, and current program participation. We will be training all of the 72 home-visitors who are being recruited through the participating home-visiting sites. Out of those 72 home-visitors, we anticipate 24 of them to implement the intervention groups and in turn be our study participants being asked to complete a semi-structured interview after the completion of their cohorts.

Study Participants: We will recruit 40 study participants from each of the 42 participating HV programs. These 40 participants per program will be recruited in five cohorts. Each cohort will be recruited for approximately one month at a participating HV program; as such, each month we recruit at a participating HV program we will only need to enroll 8 study participants (40 participants/5 cohorts).

Clinicians: We will also recruit and train ~18 clinicians to deliver MB; each clinician will deliver MB at one or more HV programs across the duration of the project. All of the clinicians who are implementing the intervention will be invited to participate in the semi-structured interviews after the completion of their cohorts. The 18 clinicians will live and work in the three different regions of Illinois where this study will be conducted: Chicago, downstate Illinois, and western Illinois, as well as adjacent states. A description of the study as well as the clinician role was sent out to the Illinois Association for Infant Mental Health (ILAIMH) listserv and the consultant email list at Illinois Children's Mental Health Partnership (ICMHP). [name], MS, the Consultation Coordinator at the Illinois Children's Mental Health Partnership (ICMHP) and coordinator of the Infant Mental Health Consultant network in Illinois, has identified clinicians from the three regions of the Illinois where this study will be conducted. We have also sent a description of the study to the Home Visiting Research Network (HVRN) to recruit adjacent states participation for wave 2 of recruitment.

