4. Of those that meet acceptable levels of imbalance, we randomly select one allocation for use in the current study.

We chose the p-value corresponding to the Kruskal-Wallis test (nonparametric version of an Analysis of Variance [ANOVA]) as our criterion for 'balance' in step #3 above. If the p-value for each of the three variables is larger than 0.30 for a given simulated allocation scheme, that particular allocation is deemed 'acceptable'. This criterion is adapted from the 'Minimal Sufficient Balance' principle from Zhao et al. [3] in the individual sequential randomization literature.

In the current study, randomization occurred in three waves for logistical purposes. The first included 14 sites (2 C:6 HV:6 MH); the second included 19 sites (4 C:7 MH:8 HV); allocation ratio was slightly off in this wave to account for dropout sites); and the third wave included 12 sites (1 C:6 MH:5 HV). Thus, we randomized a total of 45 sites in three waves; randomization of 42 sites was the study goal, reflected in our approved research plan. However, to account for site dropping out in the meantime, we adapted the algorithm to increase the number of sites randomized and also to allow for slightly discrepant allocation ratios than the planned 1:3:3 within each wave.

After randomization, eight programs dropped out, thereby yielding a total of 37 study sites contributing data for analyses. Data collected from all study participants will be used in the analysis. Among the 37 active study sites, 16 HV programs received the MB intervention delivered by mental health professionals, 15 received MB intervention delivered by HV paraprofessionals, and six programs serve as control sites. As an aside, 29 intervention sites ended up implementing at least one cohort (15 MH, 14 HV).

Statistical Methods

Descriptive statistics will summarize baseline characteristics (both site-level and participant-level) overall and by arm. As appropriate, mean \pm standard deviation (or median [inner quartile range]) will be used in cases of skewed or non-normal empirical distributions) and frequency (proportions) will summarize continuous and categorical data, respectively. Analyses will employ normal theory methodology as appropriate, and in cases of violations of assumptions, transformations and/or nonparametric analyses may be utilized.

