Analyses will proceed at the participant level. Primary analyses for QIDS-SR16 score at 24 weeks postpartum will involve all the participants in the study contributing data at this time point. Primary analyses will involve a linear mixed model for continuous outcome with independent fixed effect variables of baseline QIDS-SR16, study arm (three-level factor), and the baseline covariates listed above. We will report both covariate-adjusted and unadjusted estimates for intervention effect. Secondary analysis will be performed on those participants considered at risk at baseline (i.e., excluding the participants who do not meet the criteria for MDE as defined above). We plan to account for clustering effects via inclusion of a random site effect, which will allow for distinction of between and within-site variance. We will also explore inclusion of a random 'facilitator' effect as it is possible participants exposed to the same facilitator may have correlated responses. Intra-cluster correlation coefficients will be estimated via variance components estimates.

Intervention effect will first be evaluated via the adjusted Wald type III test for significant study arm effect at the 5% level of significance. If arm is significant at the 5% level, analyses evaluating the **superiority (Aim #1)** of HV-led intervention vs. control will proceed with Tukey's correction for multiple pairwise hypothesis tests. Assuming the Tukey-adjusted p-value for this comparison falls below the 5% level of significance in favor of the HV-led arm, **non-inferiority (Aim #2)** will further be assessed (using Tukey's correction) via pairwise comparison of adjusted 24-month QIDS in HV-led vs. MH-led arms. Figure 1 below depicts the margin and zone of non-inferiority for this comparison.

[figure not shown]

Figure 1. Margin of Non-inferiority (NI)

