We initially planned to conservatively enroll 42 sites (six controls, 18 HV-led, 18 MH-led) with a target enrollment of 40 participants per site (1680 total participants). As in any cluster-randomized trial, power and sample size considerations depend heavily on intra-cluster correlation coefficient (ICC) estimates. In general, it is recommended that these calculations account for anticipated ICC as failure to do so in the design phase and lead to an increase in type II error (i.e., result in underpowered studies) [4, 5]. Without previous knowledge of ICC(s) in this population with respect to our primary outcome, we explored a range of ICCs (0.001 to 0.05). Power calculations assume a standard deviation in primary outcome of approximately six points (on the QIDS-SR16), with a meaningful difference corresponding to five points on average across arms. Thus, for the superiority aim, we calculated power based on the average ability to detect at least a five-point mean difference between control sites and HV-led sites. Power calculations assumed a $5\%/3 = 1.7\%$ level of significance in order to account for three pairwise comparisons. This is an approach that we deem conservative as this mirrors the Bonferroni correction for multiple hypothesis tests.

We have 38 active sites: six control, 16 paraprofessional home visitor-led sites, and 16 MHP-led sites. We plan to recruit an average of 27 participants per site, allowing for up to 15% attrition (i.e., 23 participants on average for analyses). These assumptions allow for more than 95% power to detect a mean difference of five points in QIDS-SR16 across arms for an ICC of 0.01. Even if one of the six sites drops out, and if ICC is as large as 0.05 (which we deem unlikely), we still anticipate over 85% power for analyses addressing the efficacy aim (Aim #1).

Power for the NI aim will require ability to detect a smaller (margin of NI of two points) mean difference across arms. We anticipate over 90% power to detect a margin of NI of two points on the QIDS-SR16 scale if we assume an ICC of 0.01 and 16 sites in each of the intervention arms with 23 participants for analyses, on average, per site. This allows for up to 15% attrition overall. We anticipate some sites to be over/underperforming and thus unequal representation per site is inevitable. Our hope is that the precautions taken with respect to the randomization algorithm that

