attempts to control imbalance in yearly volume and population density will offset biases created by over/underrepresentation for participants at specific sites. While we do not anticipate ICC to be larger than 0.01 [4], we present the required sample size per site in Table 1 below in order to ensure 90% power under the same assumptions for all scenarios explored. We also present sample size requirements in the event that one of the active sites drops out in each of the intervention arms (i.e., 15 sites per arm). Notice that if ICC is larger than 0.02 (which we are not anticipating, although it remains possible), our projected sample size does not allow for 90% power in this case. Since these assumptions are all rather conservative, we argue adequate power for detection of both superiority and non-inferiority. Power calculations for assessment of heterogeneity of intervention effects depending on participant characteristics (Aim #3) require even more assumptions for which we have little information. Thus, we do not necessarily anticipate power to detect specific effects within subgroups or power to detect interaction effects, but we plan to use the analyses outlined here to explore these effects.

Table 1. Required Sample Size for 90% Power in Non-inferiority Aim

ICC	N HV sites	N MH Sites	N per site for analyses	N recruited per site (allowing for 15% attrition)
0.001	16	16	17	20
0.01			20	23
0.02			25	29
0.03			33	39
0.04			49	58
0.05			97	114
0.001	15	15	19	22
0.01			22	26
0.02			28	33
0.03			38	45
0.04			62	73
0.05			168	198

Technical Details

The SAP is subject to version control and we anticipate modifications to analytic plans be documented herein. As in any study, the analytic plan may change due to assumption violations, logistical issues, and/or unexpected empirical distributions of study outcomes. In these cases, the statistical analysis plan will be updated accordingly. All analyses will be performed via SAS version 9.4 or higher (The SAS Institute; Cary, NC) or R version 3.4.1 or higher (The R Foundation for Statistical Computing platform). Example t table shells are included below. Note that these are not binding and may be adapted as needed as formatting and style may be dictated by mode of dissemination or specific target journal(s) for results dissemination.

Timeline for Analyses

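### The primary model has no randomisation-wave term although the HV-to-control ratio differed by wave (6:2, 8:4, 5:1); if wave is prognostic, HV minus control is shifted by a small, avoidable amount

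*SAP*

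**What the plan says.** The SAP (Randomization Methods) plans 1:3:3 allocation of control, MH-led and HV-led sites and reports three waves. The first had 2 control, 6 HV and 6 MH sites. Then "the second included 19 sites (4 C:7 MH:8 HV); allocation ratio was slightly off in this wave to account for dropout sites". The third had 1 control, 6 MH and 5 HV sites. The unequal ratios were intended: the algorithm was adapted to "allow for slightly discrepant allocation ratios than the planned 1:3:3 within each wave". Wave is not among the three site variables used to constrain allocation.

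The primary model (SAP, Statistical Methods) contains "independent fixed effect variables of baseline QIDS-SR16, study arm (three-level factor), and the baseline covariates listed above", with a random site effect and possibly a facilitator effect. The covariates listed are participant-level. Neither wave nor calendar time enters any primary, secondary or sensitivity analysis.

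On the sites analysed, the SAP says: "After randomization, eight programs dropped out, thereby yielding a total of 37 study sites contributing data for analyses". These are 6 control, 15 HV and 16 MH sites, with no split by wave. The power section gives a different count: "We have 38 active sites: six control, 16 paraprofessional home visitor-led sites, and 16 MHP-led sites".

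The protocol (4.0 Procedures Involved) plans differently: "We will stagger implementation in two waves so that only half the sites are implementing at once". Its recruitment section (7.0) says the study was advertised through a research network "to recruit adjacent states participation for wave 2 of recruitment".

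**The concern.** When the allocation ratio differs between waves, arm and wave are associated by design. Control sites were 57% wave 2 (4 of 7) and HV sites 42% (8 of 19). This difference does not average out over repeated randomisations. A random site effect absorbs between-site variance, but it does not remove a difference in wave means between arms; conditioning on wave does.

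The contrast affected is HV minus control. It is the Aim 1 test and also the gate to the Aim 2 non-inferiority test. If wave 2 participants had worse scores, the error would favour HV; if they had better scores, it would count against HV. Unmodelled wave differences would also be counted as between-site noise and widen both intervals.

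**Working it through.** **Inputs (SAP, Randomization Methods).**

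| Arm | Wave 1 | Wave 2 | Wave 3 | Total |
|---|---|---|---|---|
| Control | 2 | 4 | 1 | 7 |
| HV | 6 | 8 | 5 | 19 |
| MH | 6 | 7 | 6 | 19 |
| All | 14 | 19 | 12 | 45 |

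The total reproduces the SAP's 45 sites.

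**Shift as randomised.** With equal site weights and an additive wave effect, shift = sum over waves of (HV share − control share) × wave mean.

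- HV shares: 6/19, 8/19, 5/19 = 0.316, 0.421, 0.263.
- Control shares: 2/7, 4/7, 1/7 = 0.286, 0.571, 0.143.
- Differences: +0.030, −0.150, +0.120.

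For wave means spanning 1 point:

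| Pattern | Absolute shift in HV − control |
|---|---|
| Only wave 2 differs | 20/133 = 0.150 |
| Only wave 3 differs | 16/133 = 0.120 |
| Only wave 1 differs | 4/133 = 0.030 |
| Linear trend (0, 0.5, 1) | 0.120 − 0.075 = 0.045 |

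For HV minus MH the share differences are 0, +1/19 and −1/19, so the shift is at most 0.053.

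**Shift in the analysed sites.** By subtraction the losses are 7 − 6 = 1 control, 19 − 15 = 4 HV and 19 − 16 = 3 MH, eight in all. I enumerated every loss pattern and took the largest shift per point in each.

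- Smallest: control 2, 3, 1 and HV 5, 8, 2. The wave 2 difference is 8/15 − 3/6 = 0.03.
- Largest: control 2, 4, 0 and HV 6, 4, 5. The wave 2 difference is 4/15 − 4/6 = −0.40.
- If losses are random, the largest shift averages 0.17 and exceeds 0.15 in about 60% of patterns. The expected signed wave 2 difference stays at −0.150.
- With the power section's 38 sites (16 HV) the range is 0.02 to 0.35; the top is 4/6 − 5/16 = 0.354.
- HV minus MH can also exceed its as-randomised 0.05. The extreme is HV 6, 8, 1 against MH 6, 4, 6: 6/16 − 1/15 = 0.31.

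**Scale.** With SD 6, 23 participants per site, ICC 0.01 (design effect 1 + 22 × 0.01 = 1.22) and 6 against 15 sites, SE = 6 × √[1.22 × (1/138 + 1/345)] = 0.67. A shift of 0.15 is 3% of the 5-point target and about 0.2 SE. A shift of 0.40 would be 8% and 0.6 SE.

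**Power and error rates.** A noncentral t with two-sided alpha 0.017, 2k − 2 degrees of freedom for k sites per arm, and design effect 1 + (m − 1) × ICC for m participants per site reproduces all 12 entries of the SAP's sample size table. It gives 93% non-inferiority power at 16 × 23 and ICC 0.01 (the SAP says over 90%).

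A simulation on site means (12,000 trials, 37 sites, 23 per site, SD 6, true differences zero, Tukey intervals) gave, without and then with wave:

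| Wave 2 shift (residual ICC) | HV − control bias | Non-inferiority power |
|---|---|---|
| 0 (0.01) | not applicable | 93.9% / 93.3% |
| 1 point (0.01) | −0.150 / 0.00 | 89.7% / 93.1% |
| 1.21 points (0) | −0.179 / 0.003 | 92.7% / 96.4% |
| 2 points (0.01) | −0.295 / 0.006 | 76.5% / 93.2% |

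The 1.21 is the wave 2 shift that by itself makes an ICC of 0.01: √[0.36 / ((19/45)(26/45))]. The 2-point row implies a total ICC of (0.36 + 0.976) / (36 + 0.976) = 0.036, where 0.976 = (19/45)(26/45) × 4.

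Two-sided type I error without wave was 3.2% to 4.3% against a nominal 5%. Superiority power at 5 points was at least 99.7% in every model.

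**The case against.** **No wave effect is shown.** This stands. Nothing in the documents says that QIDS differs by wave. A reader might take the protocol's remark on adjacent states as evidence that randomisation wave 2 is distinctive. The documents do not support that. The protocol speaks of two waves and the SAP reports three, so the remark may cover every site after the first wave. The relevant figure as randomised would then be 0.03, not 0.15. The remark makes a different site mix plausible and no more.

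**0.15 is not a bound.** A reader might treat it as the most the estimate can move per point. It is the largest as-randomised value, and it requires wave 2 to differ from both other waves. The analysed sites could give more or less. Site sizes will also be unequal, as the SAP expects.

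**The non-inferiority loss is already covered by the ICC allowance.** Largely fair. Wave variance is part of the between-site variance, the SAP explores ICCs from 0.001 to 0.05, and it discloses that 90% power is not reached above 0.02. It also writes "While we do not anticipate ICC to be larger than 0.01". If wave variance lies within that 0.01, simulated power without wave is 92.7%, still above the stated 90%. The fall to 77% needs a residual wave 2 shift of 2 points, as large as the margin itself, which nothing in the documents suggests.

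**The cost can exceed its average.** Also correct. If the lost control site was the only one in wave 3 (1 in 7 under random loss), that wave has no direct HV-control comparison, and the loss of precision is larger.

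What remains is that the ratios differed by wave on purpose and that the planned model does not condition on wave.

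**Conclusion.** The point holds at low severity. The primary analysis ignores a grouping that the randomisation itself used, with arm ratios that differed across it. Any prognostic wave effect left after the covariates would therefore shift HV minus control systematically, with the sizes per 1-point wave difference given in the working.

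The effect is small against the 5-point target. It does not inflate two-sided type I error in the simulation, and it leaves superiority power untouched. For Aim 2 the main consequence is a wider interval, to whatever extent wave variance exists.

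A reader might infer that Aim 1 is biased in favour of HV. The documents support neither the existence nor the direction of a wave effect. A reader might also extend the point to the three site variables used to constrain allocation; leaving those out is conservative and is not part of this finding.

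The figures assume equal site weights and an additive wave effect. The simulation also leaves out the participant covariates, which could absorb part of a wave effect. The average figures for the 37 sites assume that losses were random; the 0.03 to 0.40 range does not.

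**What to change.** Add randomisation wave (three levels) as a fixed effect in the primary model for the Aim 1 and Aim 2 contrasts, before database lock. Report the analysed sites by arm and wave, and settle whether there are 37 or 38. The unadjusted estimate that the SAP also promises can stay as it is.

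Only SAP wording changes, since wave is known for every site. Wave uses 2 of the 34 site-level degrees of freedom (37 sites − 3 arms). If wave is not prognostic, the standard error rises by about 1% on average. The simulated HV-control half-width goes from 1.651 to 1.676 (1.5% wider), and non-inferiority power from 93.9% to 93.3%.

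Over all loss patterns the standard error rises by at most about 6% for HV-control (control 2, 4, 0; HV 6, 4, 5; MH 6, 7, 3) and about 9% for HV-MH (control 2, 4, 0; HV 6, 8, 1; MH 6, 4, 6). The wave table should be drawn up first so that the actual cost is known.
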